### ***Medically Attended Adverse Events***

MAAEs will be collected at any time during the study.

### ***Adverse Events of Special Interest***

AESIs will be collected at any time during the study.

See [Section 8.4.9](#) for the list of AESIs.

## **8.4.5 Method of Detecting AEs and SAEs**

Individual DCs, specifically designed for this study by the Sponsor and provided to the study sites, will be given to study participants for the recording of daily safety information. These DCs will include pre-listed terms and intensity scales as well as areas for free text to capture additional safety information or other relevant details. Participants will also be provided with rulers for measuring the size of injection site reactions, and with standard digital thermometers for measuring daily temperatures. To ensure consistency of reporting, the study sites will instruct participants on how to correctly use these tools.

At specified intervals, the Investigator or an authorized designee will interview the participants to collect the information recorded in the DC and will attempt to clarify anything that is incomplete or unclear. All clinical study information gathered by the study site will be reported electronically by the Investigator or authorized designee using a web-based CRF. Any information that was not documented in the DC will first be captured in the source document and then reported electronically.

The 12-month (post-last injection) follow-up will be done by interviewing participants during a visit (or over the telephone for participants who discontinue early from the study) using a questionnaire to capture SAEs and AESIs, if applicable.

The method of recording, evaluating, and assessing causal relationship of AE and SAE and the procedures for completing and transmitting SAE reports are provided in [Appendix 10.3](#).

Care will be taken not to introduce bias when detecting AEs and/or SAEs. Open-ended and non-leading verbal questioning of the participant is the preferred method to inquire about AE occurrences.

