**Sanofi Pasteur**  
**551 - SARS-CoV-2 mRNA vaccine**

**VAW00001**  
**Protocol Version 3.0**

Visit (V)/Contact	Collection of information in the CRF	Screening visit	V01	TC1	V02	V03	TC2	V04	V05	TC3	V06	V07	V08 †††††
Study timelines (Day [D])		D(-08) to D(-01)††	D01	D03	D09	D22	D24	D30	D36	D43	D112	D202	D387
Time interval (days)		V01 – (1 to 8 days)		V01 + 2 days	V01 + 8 days	V01 + 21 days	V03 + 2 days	V03 + 8 days	V03 + 14 days	V03 + 21 days	V03 + 90 days	V03 + 180 days	V03 + 365 days
Time windows (days)			N/A	N/A	[+2 days]	[+7 days]	N/A	[+2 days]	[+7 days]	[+2 days]	[+7 days]	[+14 days]	[+14 days]
Visit procedures:													
Active surveillance calls	X										TC to occur every 2 weeks (± 6 days) after the D43 contact until D202††††† (See also Schedule of Activities Table 1.6 for follow-up)		
Collection of SAEs, AESIs§§§§, and MAAEs	X		To be reported at any time during the study										
Collection of pregnancies	X												
End of phase participation record*****	X									X	X	X	
End of active phase participation record	X												X
12 month post-VAC2 follow-up participation record (only for those	X												X

Sanofi Pasteur  
551 - SARS-CoV-2 mRNA vaccine

VAW00001  
Protocol Version 3.0

Visit (V)/Contact	Collection of information in the CRF	Screening visit	V01	TC1	V02	V03	TC2	V04	V05	TC3	V06	V07	V08 †††††
Study timelines (Day [D])		D(-08) to D(-01)††	D01	D03	D09	D22	D24	D30	D36	D43	D112	D202	D387
Time interval (days)		V01 – (1 to 8 days)		V01 + 2 days	V01 + 8 days	V01 + 21 days	V03 + 2 days	V03 + 8 days	V03 + 14 days	V03 + 21 days	V03 + 90 days	V03 + 180 days	V03 + 365 days
Time windows (days)			N/A	N/A	[+2 days]	[+7 days]	N/A	[+2 days]	[+7 days]	[+2 days]	[+7 days]	[+14 days]	[+14 days]
Visit procedures:													
discontinued early) †††††													

Abbreviations: Ab, antibody; AE, adverse event; AESI, adverse event of special interest; BL, blood sample (#); CRF, Case Report Form; D, Day; DC, Diary Card; HIV, human immunodeficiency virus; IRT, Interactive Response Technology; MAAE, medically attended AE; PT, prothrombin time; PTT, partial thromboplastin time; SAE, serious adverse event; SARS-CoV-2, severe acute respiratory syndrome coronavirus 2; TC, telephone call; V, Visit; VAC, Vaccination.

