‡‡ Participants will use this DC1 to record information about solicited reactions, unsolicited AEs, SAEs, and AESIs from D01 to D08 after vaccination and will continue to record information about unsolicited AEs, SAEs, and AESIs from D09 to V03.

§§ The Investigator or an authorized designee will remind the participants to bring back the DC at the next visit and will answer any questions.

\*\*\* The Investigator or an authorized designee will interview the participants to collect the information recorded in the DC and will attempt to clarify anything that is incomplete or unclear.

††† Participants will use this DC2 to record solicited reactions, unsolicited AEs, SAEs, and AESIs (from V03 to V04) and will continue to collect unsolicited AEs, SAEs, and AESIs (from V04 to V05).

‡‡‡ Participants will use this DC3 for unsolicited AE follow-up until D43, and SAE follow-up (including AESIs) and COVID-19-like illness follow-up from V05 to V06.

§§§ Participants will use this DC4 for SAE follow-up (including AESIs) and COVID-19-like illness follow-up from V06 to V07.

\*\*\*\* Participants will use this DC5 for SAE follow-up (including AESIs) and COVID-19-like illness follow-up from V07 to V08.

†††† During the D43 telephone call, staff will review the DC3 pertaining to unsolicited AEs, SAE, AESI, and COVID-19-like illness between V05 and the call (data will be entered in the CRF) and will remind the participants to bring back the DC3 for V06. The D03 and D24 telephone calls will NOT be reported in the CRF (ie, only the data obtained from these telephone calls will be reported in the CRF).

‡‡‡‡ The frequency of phone contacts will be once every 2 weeks ( $\pm$  6 days) or may be completed through alternative contact methods (text message, email, and/or home visit). Prior to these specified time-points, active surveillance will still occur during the established contacts (phone calls and visits).

§§§§ AESIs (serious and non-serious) will be collected throughout the study as SAEs to ensure that events are communicated to the Sponsor in an expedited manner and followed-up until the end of the follow-up period or resolution, as per the assigned causal relationship. These include protocol-specified AESIs: anaphylactic reactions, generalized convulsion, Guillain-Barré Syndrome, acute disseminated encephalomyelitis, thrombocytopenia, vasculitides, any new-onset chronic medical conditions, and AESIs related to SARS-CoV-2 infection and COVID-19 disease.

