\*\*\*\*\* In case of participant discontinuation at a visit, the entire visit will be completed.

††††† All participants will be scheduled to attend V08 for blood sampling and 12-Month (post-VAC2) Safety Follow-up. However, if any participants discontinue the study early, they are still to be followed for safety and are to be contacted with a Safety Follow-up call to identify the occurrence of any SAEs and AESIs that had not yet been reported. If discontinuation occurs at a scheduled visit, the participant will be provided a Memory Aid instead of a DC for SAE follow-up (including AESIs) until the Safety Follow-up call. If a participant discontinues between visits (with no Memory Aid provided yet), the participant will use the last DC received to collect information for the Safety Follow-up call.

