**Table 3.1: Objectives and endpoints**

Objectives	Endpoints
Primary	

Safety
 
To describe the safety profile of all participants in each age group and each study intervention group up to 12 months post-last dose.
	
Safety
 
 
• Presence of unsolicited systemic AEs reported in the 30 minutes after each injection
 
• Presence of solicited injection site reactions and systemic reactions (pre-listed in the participant's Diary Card [DC] and Case Report Form [CRF]) occurring up to 7 days after each injection
 
• Presence of unsolicited AEs reported up to 21 days after each injection
 
• Presence of medically attended adverse events (MAAEs) throughout the study
 
• Presence of serious adverse events (SAEs) and adverse events of special interest (AESIs) throughout the study
 
• Presence of out-of-range biological test results up to 8 days post-last dose (ie, up to Day [D] 09 for Cohort 1 and up to D30 for Sentinel Cohort and Cohort 2)
 

Objectives	Endpoints

Immunogenicity
 
To describe the neutralizing antibody profile at D01, D22, and D36 of each study intervention group.
	
Immunogenicity
 
Neutralizing antibody titers against the SARS-CoV-2 D614G variant will be measured with the neutralization assay
 
 
• Antibody titer at D01, D22, and D36
 
• Fold-rise (fold-rise in serum antibody neutralization titer post-vaccination relative to D01) at D22, and D36
 
• 2-fold and 4-fold-rise in serum neutralization titer (post/pre) relative to D01 at D22, and D36
 
• Occurrence of neutralizing antibody seroconversion defined as baseline values below lower limit of quantification (LLOQ) with detectable neutralization titer above assay LLOQ at D22 and D36
 

Secondary	

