#### 8.4.10 Medically Attended Adverse Events

Medically-attended AEs will be collected using the same process as other AEs. See [Appendix 10.3.1](#) for definition of MAAEs.

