5.1.1.2 Statistical Methods for Primary Safety Objective

The following safety parameters will be used for the evaluation of safety. Additional parameters may be displayed as appropriate.

Solicited Reactions

Number and percentage of participants with:

- Presence of solicited injection site reactions and systemic reactions occurring up to 7 days after injection
- Each solicited reaction according to time of onset, maximum intensity, and number of days of occurrence over the solicited period

Unsolicited Events and Reactions

Number and percentage of participants with:

- Any unsolicited immediate systemic event in the 30 minutes after injection
- Any unsolicited event and reaction (using the current MedDRA version) 21 days after injection
- Any unsolicited event/reaction according to time of onset, maximum intensity, and duration

SAEs

Number and percentage of participants with:

- Any SAE within 21 days after injection and throughout the entire study according to SOC and PT, seriousness, and outcome

AESIs

Number and percentage of participants with:

- Any AESI within 21 days after injection and throughout the entire study according to SOC and PT, seriousness, and outcome

MAAEs

Number and percentage of participants with:

- Presence of MAAEs within 21 days after injection and throughout the entire study

Laboratory tests

- Presence of out-of-range biological test results up to 8 days post-last dose (ie, up to D09 for Cohort 1 and up to D30 for Sentinel Cohort and Cohort 2)
- Summary of toxicity grade shift from baseline

For descriptive purposes, the statistics presented in [Table 5.1](#) will be produced for the above safety parameters for each intervention group and each age group. The same dose-level group in Sentinel Cohort and Cohort 2 will also be pooled for analysis.

Harm analysis

Harm analysis assessed based on split of COVID-19 case will be assessed based on Safety Analysis Set (SafAS) at the time of the final analysis. Participants will be analyzed according to the study intervention they received. For the assessment, all dose-level arms will be pooled, and all placebo arms will be pooled as well.

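### Medically attended adverse events are a whole-study primary safety endpoint, but after D22 (Cohort 1) or D43 (Sentinel, Cohort 2) no follow-up tool described in the protocol names them

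*Protocol*

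**What the plan says.** **Endpoint and analysis.** Protocol Table 3.1 lists "Presence of medically attended adverse events (MAAEs) throughout the study" among the primary safety endpoints. SAP Section 5.1.1.2 plans the number and percentage of participants with "Presence of MAAEs within 21 days after injection and throughout the entire study".

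**Duty to collect.** Protocol Section 8.4.4 states "MAAEs will be collected at any time during the study". The schedules of activities (Tables 1.3 to 1.5) put SAEs, AESIs and MAAEs in one row, marked "To be reported at any time during the study". Section 8.4.10 adds "Medically-attended AEs will be collected using the same process as other AEs".

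**Tools.** Section 8.4.4 limits non-serious unsolicited AEs to the 21 days after each injection. The tools described for the time after that are:

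- *Diary cards.* For the Sentinel Cohort, the Table 1.3 footnotes say "Participants will use this DC4 for SAE follow-up (including AESIs) and COVID-19-like illness follow-up from V06 to V07". DC5 follows the same pattern, as does DC3 once its unsolicited-AE part ends at D43. Cohort 2 (Table 1.5) matches this. In Cohort 1 (Table 1.4) the pattern starts with DC2, at D22.
- *Two-weekly calls.* These ask about COVID-19-like illness and run until D181 (Cohort 1) or D202 (Sentinel, Cohort 2).
- *12-month follow-up.* Section 8.4.5 describes an interview "using a questionnaire to capture SAEs and AESIs, if applicable".
- *Early discontinuation.* Participants receive a "Safety Follow-up call to identify the occurrence of any SAEs and AESIs that had not yet been reported". The Memory Aid given to those who leave at a visit has the same scope.

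**The concern.** SAEs, AESIs and MAAEs carry the same whole-study duty, but the tools treat them differently. The first two are named in the later cards, the questionnaire and the discontinuation call. MAAEs are named in none of these.

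Section 8.4.10 does not close the gap. It sends MAAEs to the general AE process, and for non-serious events that process stops 21 days after the last injection.

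What is left without a named prompt is the late MAAE that is non-serious, not an AESI and not a COVID-19-like illness. Section 10.3.1 counts even a telephone or email contact with a physician as a visit for MAAE purposes. Contacts of that kind are easily left unmentioned months later unless someone asks.

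At stake is the whole-study MAAE percentage, a primary safety result of a first-in-human product. It would mix a prompted early window with a long later period in which capture depends on what participants volunteer and how sites ask.

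**Working it through.** **Inputs**

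- Last planned visit: D366 (Cohort 1), D387 (Sentinel, Cohort 2), from Tables 1.3 to 1.5.
- End of unsolicited-AE collection: D22 (Cohort 1), D43 (Sentinel, Cohort 2), from the same tables and Section 6.5.
- Six-month visit: D181 (Cohort 1), D202 (Sentinel, Cohort 2).
- Follow-up shortened to 6 months: SAP Sections 1 and 5.7.

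**Reproducing the plan's durations.** Duration = last visit day − 1. This gives 366 − 1 = 365 and 387 − 1 = 386 days, matching the durations in the synopsis and Table 4.1.

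**Share of follow-up without a named MAAE prompt** = (last day − last day of unsolicited-AE collection) / duration.

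| Follow-up | Cohort 1 | Sentinel and Cohort 2 |
|---|---|---|
| Planned 12 months | (366 − 22)/365 = 344/365 = 94.2% | (387 − 43)/386 = 344/386 = 89.1% |
| 6 months, per SAP | (181 − 22)/180 = 159/180 = 88.3% | (202 − 43)/201 = 159/201 = 79.1% |

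**Pooled over the planned 333 participants** (154 in Cohort 1; 154 + 25 = 179 in Cohort 2 and the Initial Sentinel Cohort):

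- 12 months: 333 × 344 / (154 × 365 + 179 × 386) = 114,552/125,304 = 91.4%.
- 6 months: 333 × 159 / (154 × 180 + 179 × 201) = 52,947/63,699 = 83.1%.
- With all 75 Sentinel participants (383 in total) the figures are 91.1% and 82.6%.

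**Sensitivity.** If the second injection falls at the end of its 7-day window, the unprompted time is still 344 days and the duration becomes 386 + 7 = 393, so the share is 344/393 = 87.5%.

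**Contact density.** In the 12-month plan the two-weekly calls stop at D181 or D202. The next planned contact is 366 − 181 = 387 − 202 = 185 days later, and DC5, which does not name MAAEs, is the card in use for that interval.

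**What the arithmetic does not give.** The documents state no MAAE rate and no capture fraction with or without a prompt, so the number of events missed cannot be calculated.

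**The case against.** Several points on the other side stand.

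- **Collection is required throughout.** Section 8.4.5 gives the cards free-text areas, has staff interview participants at set intervals, and prefers open-ended questions. Card-collection interviews take place at D91/D112, D181/D202 and D366/D387. This is partial capture, so it would be wrong to read the plan as collecting no MAAEs after D43.
- **The later cards are not confined to SAEs and AESIs.** They also cover COVID-19-like illness, and Section 8.2.2.2 collects health-care use for reported illnesses. AESIs include new-onset chronic conditions and a long organ-system list. The unprompted remainder is therefore narrower than all late MAAEs.
- **The tools themselves are not in the documents.** The footnotes summarise the cards and may be incomplete. The DC1 footnotes omit COVID-19-like illness, although Section 8.2.2.2 refers to illness symptoms listed in the diary card. The finding therefore concerns the tools as described. Even so, the DC1 and DC2 footnotes for Sentinel and Cohort 2 include unsolicited AEs, which would take in MAAEs; the later ones do not.
- **Follow-up changed.** SAP Sections 1 and 5.7 report that after 27 September 2021 safety calls monitored MAAEs, and that the study was later ended at 6 months.
- **The analysis is descriptive.** MAAEs within 21 days are tabulated separately, so the prompted window can be read alone.

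A reader might infer from the 89% to 94% that this share of MAAEs is missed. The documents do not support that: the figure is calendar time without a named prompt.

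**Conclusion.** The mismatch stands. The protocol sets a whole-study primary endpoint, and the tools it describes for most of follow-up do not ask for part of it. Under-reporting of late MAAEs that are non-serious, not AESIs and not COVID-19-like illness is likely, but its size is unknown.

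Time without a named prompt is 94% (Cohort 1) and 89% (Sentinel, Cohort 2) of the planned 12 months. Under the 6-month follow-up it is 88% and 79%. These last two are upper figures, because an unstated part of that time was covered by safety calls that monitored MAAEs.

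The figures assume on-schedule visits and follow-up not cut short. The SAP's main safety analysis drops events with onset on or after receipt of an authorized vaccine, which shortens the later period for those participants. The conclusion also assumes that the footnotes and Section 8.4.5 reflect what the tools ask.

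The safety calls add a second issue. Ascertainment may have changed partway through, under the same decision that called for unblinding participants, yet the SAP tabulates MAAEs only within 21 days and over the whole study. This deserves correction, but it does not show that the primary safety conclusions are wrong.

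**What to change.** **In the protocol and its tools:** name MAAEs in DC2 to DC5 for Cohort 1, DC3 to DC5 for the Sentinel Cohort and Cohort 2, the Memory Aid, the follow-up questionnaire, the early-discontinuation call and the existing two-weekly calls. No new contact is needed. The cost is wording changes and slightly more reporting work for participants and sites.

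**In the final analysis:** since vaccination and enrollment have stopped, this is the part that can still help the present study. Report MAAEs by ascertainment period (within 21 days of injection, later scheduled follow-up, safety-call period) and state how they were sought in each. This adds a few table rows and a short methods statement. If the tools in the Operating Guidelines did ask about MAAEs, saying so there would settle the point.

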## **8.4.6 Follow-up of AEs and SAEs**

Unless a participant refuses further contact, each participant who experiences an AE (whether serious or non-serious) during the study must be followed until the condition resolves, becomes stable, or becomes chronic (even after the end of the participant's participation in the study) if *either* of the following is true:

- The AE is considered by the Investigator to be related to the study intervention administered
- The AE caused the discontinuation of the participant from the study or from vaccination

The Investigator will inform the Sponsor of the date of final disappearance of the event or the date of "chronicity" establishment.

#### 8.4.7 Regulatory Reporting Requirements for SAEs

- Prompt notification by the Investigator to the Sponsor of an SAE is essential so that legal obligations and ethical responsibilities towards the safety of participants and the safety of a study intervention under clinical investigation are met.
- The Sponsor has a legal responsibility to notify both the local regulatory authority and other regulatory agencies about the safety of a study intervention under clinical investigation. The Sponsor will comply with country-specific regulatory requirements relating to safety reporting to the regulatory authority, IRB/IEC, and Investigators.
- For all studies except those investigating medical devices, Investigator safety reports must be prepared for suspected unexpected serious adverse reactions (SUSAR) according to local regulatory requirements and Sponsor policy and forwarded to Investigators as necessary.
- An Investigator who receives an Investigator safety report describing an SAE or other specific safety information (eg, summary or listing of SAEs) from the Sponsor will review and then file it and will notify the IRB/IEC, if appropriate according to local requirements.

#### 8.4.8 Pregnancy

Pregnancy is an exclusion criterion for enrollment in this study, but a participant could potentially become pregnant during her participation.

- Details of all pregnancies in female participants will be collected by the Investigator after the start of study intervention and until delivery and recorded in the Pregnancy CRF. Any data collected after CRF lock will be transmitted to the pharmacovigilance department on the paper form.
- The collection period of pregnancy information will correspond at least to the period during which the participant is requested to be under contraception. (according to protocol: effective method of contraception or abstinence from at least 4 weeks prior to the first vaccination until at least 12 weeks after the last vaccination). If there are any pregnancies during this period, follow-up should be conducted up to delivery: this will be covered by the 12-month surveillance of the study.
- If a pregnancy is reported, the Investigator should inform the Sponsor within 1 month of learning of the pregnancy and should follow the procedures outlined in [Appendix 10.4](#).
- Abnormal pregnancy outcomes (eg, spontaneous abortion, fetal death, stillbirth, congenital anomalies, ectopic pregnancy) are considered SAEs.

#### 8.4.9 Adverse Events of Special Interest

AESIs will include:

- Protocol-specified AESIs: Anaphylactic reactions, generalized convulsion, Guillain-Barré Syndrome (GBS), acute disseminated encephalomyelitis (ADEM), thrombocytopenia, and vasculitides
- New-onset chronic medical conditions (NOCMCs)

- AESIs related to SARS-CoV-2 infection and COVID-19 disease (see [Appendix 10.5](#)).

#### 8.4.10 Medically Attended Adverse Events

Medically-attended AEs will be collected using the same process as other AEs. See [Appendix 10.3.1](#) for definition of MAAEs.

### 8.5 Treatment of Overdose

Since the study intervention is administered by a health care professional, it is unlikely that overdose by injection occurs.

However, in the event of an overdose, the Investigator should:

- 1) Contact the RMO immediately
- 2) Closely monitor the participant for any AE/SAE
- 3) Document the quantity of the excess of the overdose in the source documents

